The additional pre-operative investigations will be co-ordinated with the preassessment team to minimize changes to the normal patient pathway. If patients have already had pre-operative investigations required as part of the study protocol prior to enrolment, the data from these investigations may be used for the purposes of research.

Clinical history and examination- Patients will be reviewed at initial surgical consultation, 6-8 weeks after surgery and one year after surgery.

Right heart catheterisation- It is the usual gold standard practice at our institution for patients to have a right heart catheterisation before being referred for surgery. The few patients who have not had one before surgery will be referred to the Department of Pulmonary Hypertension at Hammersmith Hospital for this test to be performed.

Cardiac MRI- patients will have a T1 weighted non-contrast cardiac MRI. One strength of cardiac MRI over transthoracic echocardiogram is the ability to provide objective measurements of right heart function. Parameters measured will be left and right ventricular ejection fraction, cardiac chamber dimensions, patterns of myocardial fibrosis.

Cardiopulmonary exercise testing (CPET)- CPET is a quantitative and validated method of assessing cardiorespiratory function and exercise capacity with commonly measured variables including maximal oxygen consumption (VO2 max) and the clearance of carbon dioxide during exercise (Ve/VCO2). The patient's gaseous exchange is monitored during a 3 minute rest period, a three minute "rolling basal" period when they perform exercise on a bicycle with no load; and subsequently during the exercise phase when the work load increases at a rate of 30 Watts per minute. The exercise continues until the patient has to stop or predicted maximum heart rate is achieved.

Pulmonary function tests- Patients will have routine spirometry tests and also assessment of transfer factor (DLCO and KCO). It is normal practice for patients to have spirometry at preassessment clinic and those with abnormal spirometry or a significant history of respiratory disease to have transfer factor measured.

Transthoracic echocardiogram- It is normal practice for patients to have a transthoracic echocardiogram at preassessment clinic to assess biventricular function, dimensions and cardiac structural disease.

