3.1 STUDY OUTCOME MEASURES

- 1. The accuracy of transthoracic echocardiogram compared to right heart catheterization in measuring pulmonary artery pressures in a prospective severe mitral valve disease cohort.
- Correlation between objective measurements of exercise capacity on cardiopulmonary exercise testing with quality of life and measurement of cardiac function on transthoracic echocardiogram and cardiac MRI in severe mitral valve disease.
- 3. Histological changes in the left and right ventricle in severe mitral valve disease.
- Pilot data on changes in exercise capacity and quality of life and relationship to transthoracic echocardiogram, cardiac MRI and pulmonary function tests early after mitral valve surgery.

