4.3 EXCLUSION CRITERIA

Age <18 years or >85 years, pregnancy, critical preoperative status with multi-organ dysfunction, emergency cardiac surgical intervention, unable to give informed consent or unwilling to participate in research, patients with definite contraindication for MRI would be excluded from the cardiac MRI element of the study, patients unable to take adequate biopsies due to technical difficulties would be excluded from the myocardial biopsy element of the study, other significant valve lesions requiring concomitant surgery.

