7. STATISTICS AND DATA ANALYSIS

The myocardial specimens will be preserved in formalin and transferred to the pathology laboratory at Hammersmith Hospital for processing and histological analysis. Spare sections will be fixed in Polysine slides and stored in the pathology laboratory at Hammersmith Hospital.

All data will be expressed as mean with standard error. Statistical comparison will be performed by one-way ANOVA followed by unpaired t-test as appropriate. Results will be considered statistically significant if P<0.05.

Data and all appropriate documentation will be stored for a minimum of 10 years after the completion of the study at Imperial College.

8. **REGULATORY ISSUES**

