this outcome we have run univariable and multivariable logistic regression model. In consideration of the fact that the overall number of events for this outcome was limited, the final multiple model was a parsimonious model developed using a meaningful selection of the variables that were considered relevant in previous published research (preoperative LVEF \leq 60 %, LVESD \geq 40 mm and ppVO2 % $\leq 84\%$) plus the class of surgical indication.

Correlation between TTE parameters and MRI parameters

Linear models have been run to compare some TTE parameters with the same MRI models.

Comparing changes in quality of life between class of indication of surgery Linear mixed effects models were fitted for longitudinal (repeated measures) outcomes (physical functioning and social functioning) adjusted for time, preoperative percentage predicted peak VO2, preoperative LVEDD and preoperative LVESD.

For each of the main outcomes a stepwise approach has been used to model the data: first, an unconditional means model was run to describe the data and to test the null hypothesis; then an Unconditional Growth Model to set up the slope has been run followed by a Conditional Growth model (to set up the intercept). The unconditional mean model determines if the intercept is different from zero and if there is subjectrelated variability. The unconditional growth model can have a fixed or a random slope: the fixed slope is based on the assumption that each individual in the dataset is following a similar pattern over time, while the random slope allows individual variability. Both models have been run to find out the best fitting model. The Conditional growth model is the final step and it is the complete final model adjusted for the covariates. All models were fitted using maximum likelihood methods.

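### Linear models alone show association, not agreement, between TTE and cardiac MRI; add paired differences and limits of agreement to this ancillary analysis

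*SAP*

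**What the plan says.** The SAP gives this comparison one sentence, under the heading "Correlation between TTE parameters and MRI parameters": "Linear models have been run to compare some TTE parameters with the same MRI models". I take the last words to mean the same parameters measured on MRI. The sentence does not name the parameters or the time point. It does not say which method is the outcome, or how slope, intercept or fit will be read. The SAP plans no mean difference, limits of agreement or errors-in-variables regression.

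The protocol shows which parameters could be paired. Section 3 says of MRI: "Parameters measured will be left and right ventricular ejection fraction, cardiac chamber dimensions, patterns of myocardial fibrosis". It describes the routine "transthoracic echocardiogram at preassessment clinic to assess biventricular function, dimensions and cardiac structural disease". Ventricular function and chamber dimensions are therefore available from both methods, while fibrosis patterns are listed for MRI only. Section 3 and Appendix 1 place both scans before surgery and again at 6-9 months.

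The planned sample is 50 patients (Study Summary). The paired sample may be smaller, because "patients with definite contraindication for MRI would be excluded from the cardiac MRI element of the study" (section 4.3).

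**The concern.** When one quantity is measured by two methods that both carry error, the natural question is how far apart the readings are in the same patient. A linear model answers a different question: whether patients who read high on one method also read high on the other. A clearly significant slope is then expected even if the methods differ by a fixed amount or scatter widely. A slope below 1 can also look like disagreement when there is no systematic difference.

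At stake is how a reader interprets the word compare. LVEF cut-offs recur in the study: 60% for the groups in protocol section 3, 60% for a predictor in the SAP's logistic model, and 50% for part of its dichotomous outcome. A reader may take a strong TTE-MRI correlation as reassurance that either method would classify a patient the same way at these values. The planned analysis cannot give that reassurance.

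**Working it through.** The documents give no figure for this comparison, so there is nothing to reproduce. What follows shows what a linear model would and would not reveal.

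**Inputs.** From the documents: n = 50 and a 5% significance level (protocol section 7; two-sided assumed). Assumed, because neither document gives them: true LVEF mean 60 and SD 8 points (variance 64); independent random error, SD 3 for MRI and 4, 6 or 8 for TTE; constant TTE offset of 0, 5 or 10 points.

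**Slope, correlation and limits with no offset.**
- Slope of MRI on TTE = 64/(64 + TTE error variance)
- Slope of TTE on MRI = 64/(64 + MRI error variance) = 64/73 = 0.88 throughout
- r = 64/√[(64 + TTE error variance) × 73]
- 95% limits of agreement = ±1.96 × √(TTE error variance + 9)

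| TTE error SD | Slope, MRI on TTE | Slope, TTE on MRI | r | Limits (points) |
|---|---|---|---|---|
| 4 | 64/80 = 0.80 | 0.88 | 0.84 | ±9.8 |
| 6 | 64/100 = 0.64 | 0.88 | 0.75 | ±13.1 |
| 8 | 64/128 = 0.50 | 0.88 | 0.66 | ±16.7 |

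Every row has zero systematic difference, yet every slope is below 1. How far below depends on which method is the predictor, and the SAP does not say. With an error-free predictor the expected slope is 1.

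**Constant offset.** Adding 5 or 10 points to TTE changes no variance or covariance, so slope and r stay as tabulated. Only the intercept moves (TTE error SD 4):
- TTE on MRI: (60 + offset) − 0.877 × 60 = 7.4, 12.4, 17.4 for offsets 0, 5, 10.
- MRI on TTE: 60 − 0.80 × (60 + offset) = 12, 8, 4. Here the intercept approaches zero as the offset grows.

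The intercept therefore carries the offset, but mixed with attenuation.

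**Simulation (TTE on MRI, 20,000 replicates, n = 50).**
- No offset, equal error SDs of 3, 5 and 8 in the two methods: mean slope 0.88, 0.72 and 0.50. The 95% CI lies wholly below 1 in 41%, 78% and 97% of runs.
- No offset, error SD 5 in both: the intercept differs significantly from zero in 77% of runs. The paired mean difference rejects in 5%, as it should.
- Error-free MRI, TTE error SD 5, true offset 5: the intercept differs from zero in 15% of runs; the paired difference detects the offset in 100%.
- Error SD 5 in both, offset 5: the paired difference detects it in 99.9% of runs at n = 50 and 96% at n = 30.

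**Classification at 60%, if both methods were used there.** With no offset, the share of patients on opposite sides of 60 is arccos(r)/π = 18%, 23% and 27% for TTE error SD 4, 6 and 8. At TTE error SD 4, a 10-point offset raises 18% to 37% (bivariate normal), while r stays at 0.84.

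**The case against.** The strongest reply is that the plan promises no agreement analysis. The section is headed as a correlation, and no objective or outcome in either document concerns TTE-MRI agreement. The protocol's method-accuracy outcome is a different pair: "The accuracy of transthoracic echocardiogram compared to right heart catheterization in measuring pulmonary artery pressures". This stands, and it limits the point to an improvement.

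Three stronger readings are tempting but not supported.
- **That a linear model cannot see a constant offset.** It is not hidden from the model as such, since it moves the intercept. If the SAP's means and SDs were tabulated for both methods, an average offset would also show roughly, subject to patients without MRI missing from one column. Neither source gives the within-patient spread, and the SAP does not say that the intercept will be read.
- **That unreliable LVEF classification follows.** Neither document says whether TTE or MRI supplies the LVEF at 60% and 50%, or that LVEF is among the compared parameters. The comparison feeds no stratum, predictor or outcome.
- **That the word some signals selective reporting.** It may only mean the parameters that both methods measure. The list is open, but selection is not shown.

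It is also fair to say that quoting only MRI on TTE would show the steeper attenuation. The reverse direction, with the same SDs, gives 0.88, so both are shown.

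**Conclusion.** The point holds as a limited one. For the same parameter measured by TTE and MRI, the planned linear models can support a statement about association and cannot support one about agreement. Nothing else in the SAP fills that gap. The directions follow from least-squares theory: an offset leaves slope and r unchanged, and error in the predictor lowers the slope. The sizes, including slopes of 0.80 to 0.50 or 0.88 and limits of about ±10 to ±17 LVEF points, depend on the assumed SDs and on independent errors.

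No primary result is affected. The change is worth making because it uses data already collected and answers the question most readers will bring to a TTE-MRI comparison.

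**What to change.** Keep the linear models if wanted, state which method is the outcome, and label them as association. For each parameter measured by both methods (for example LVEF and chamber dimensions; list them in the SAP), separately before surgery and at 6-9 months:
1. Report the paired mean difference with its 95% CI, and the 95% limits of agreement with CIs.
2. Check whether the difference varies with the mean of the two methods.
3. If LVEF is included, count patients classified differently at 60% and at 50%.
4. If a calibration line is wanted, use Deming regression and state the error-variance ratio assumed.

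The cost is a few lines of SAP text and a little more analysis; no new data are needed. The drawback is imprecision. With n = 50, the 95% CI around each limit is roughly ±1.96 × √(3/50) × SD of the differences. That is ±2.4 points when the SD is √(16 + 9) = 5, and ±4.1 when it is √(64 + 9) = 8.5. It is wider with fewer MRI patients.

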Quality of life questionnaire- At the preassessment clinic, patients will be asked to fill out a validated quality of life questionnaire (SF-36 health survey).

Intra-operative specimens

Heart muscle biopsies will be obtained at the time of clinically indicated heart surgery. Two small heart samples approximately 0.8 grams each or the size of a cooked rice grain will be taken from the left and right ventricle. The specimens will be preserved in formalin and processed and analysed at the Department of Pathology by a pathologist with a specialist interest in cardiac pathology. The samples will be fixed and analysed with haematoxylin and eosin for structure, Elastin van Gieson stain for elastin, Martius, Scarlet and Blue stain for fibrin, Picrosirius red stain for collagen, Perls' Prussian blue stain for iron, Periodic acid-Schiff stain for polysaccharides, Desmin stain for smooth muscle, CD68 for monocytes, CD45 for leucocytes, smooth muscle actin for smooth muscle and CD31 for vascular endothelium.

[name] 22/12/16 16:42 Deleted: 2 [name] 22/12/16 16:43 Deleted: 1 [name] 22/12/16 16:43 Deleted: 9

By correlating the results of the histological analysis with clinical markers such as left and right ventricle function and pulmonary hypertension, and the cardiac imaging on transthoracic echocardiogram and cardiac MRI this will enable us to grade microscopic changes in the myocardium throughout the spectrum of mitral valve disease from asymptomatic to symptomatic.

In addition, the results of the histological analysis will be the basis of further collaborative work with the Myocardial Function group at the Imperial Centre for Translational and Experimental Medicine.

Post-operative follow up

6-8 weeks- it is normal practice for patients to be reviewed at 6-8 weeks after surgery in clinic with clinical history and examination. Patients will be asked to fill in a quality of life questionnaire at this time.

6-9 months- Patients will have a repeat transthoracic echocardiogram, cardiac MRI, CPET, pulmonary function tests. A quality of life questionnaire will be mailed to patients with a self-addressed envelope.

12 months- it is normal practice for patients to be followed up at 12 months after surgery with clinical history and examination.

Review of investigations

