RIPCOM 1

The right ventricular pulmonary circulation in mitral valve disease study 1

Statistical methods

Version 1 31/12/2016 IRAS ID 199676

MAIN SPONSOR: Imperial College London FUNDERS: Applications to Heart Research UK, Rosetrees Trust and British Heart Foundation pending STUDY COORDINATION CENTRE: Department of Cardiothoracic Surgery, Hammersmith Hospital NRES reference: 199676

Protocol authorised by:

Name & Role	Date	Signature
[name]	31/12/16	
[name]	31/12/16	
[name]	31/12/16	

Statistical methods

Data are presented as mean \pm SD for continuous numerical variables and as count and percentages for categorical variables. Normality was assessed with Lilliefors (Kolmogorov-Smirnov) normality test: for consistency in reporting the data we have reported the numerical variables as mean \pm SD regardless their distribution. We compared the pre-operative characteristics, echocardiographic characteristics and CPET variables between class 1 and class 2 diagnosis with Student t-test for normally distributed numerical variables and Mann-Whitney (Wilcoxon) test for not normally distributed numerical variables. The comparison between categorical variables was conducted with Chi-square test or Fisher Exact test as appropriate. The CPET results before and after surgery have been compared using paired t-test or paired Wilcoxon test depending on the distribution.

Primary Outcome: reduced functional capacity at follow up

This was a per protocol analysis. To identify the predictors of reduced functional capacity we have run two different types of regression models. In the first model (linear regression) we have treated our outcome (VO2 % at follow up) as a numerical continuous variable. The predictors were evaluated trough a univariable analysis first and then a multiple model was run including those predictors that appeared to be significant at univariable analysis. The final model was obtained via a backward selection using AIC (Aikake Information Criterion) as criterion.

In the second model, the outcome was defined as a dichotomic variable that included a VO2% of $\leq 84\%$ and/or LVEF $\leq 50\%$ at follow up. To evaluate the predictors of

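### The quality-of-life mixed model is headed as a comparison of changes between classes of surgical indication, but states no class-by-time term.

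*SAP*

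**What the plan says.** The SAP section is headed "Comparing changes in quality of life between class of indication of surgery". It fits linear mixed models to two repeated outcomes, physical functioning and social functioning, "adjusted for time, preoperative percentage predicted peak VO2, preoperative LVEDD and preoperative LVESD". The models are built in three steps: an unconditional means model, an unconditional growth model for the slope, and then a "Conditional Growth model (to set up the intercept". Of this last step the SAP says that "it is the complete final model adjusted for the covariates". For the slope, a fixed and a random version are compared: "Both models have been run to find out the best fitting model". The random version is described as allowing for variation between individuals.

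Elsewhere the SAP does write class into an analysis. The logistic model for the primary outcome takes three named predictors "plus the class of surgical indication", and the opening paragraph compares pre-operative, echocardiographic and CPET variables "between class 1 and class 2 diagnosis".

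The protocol (section 3 and Appendix 1) collects the questionnaire before surgery, at 6-8 weeks and at 6-9 months. Section 7 of the protocol gives only one-way ANOVA and t-tests and has no quality-of-life model.

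**The concern.** A comparison of change between groups needs a term that lets the time effect differ by group. None is stated in the SAP or in protocol section 7. The growth-model sequence does not supply it. The slope is set before any covariate enters, the conditional step is tied to the intercept, and the random slope describes differences between patients, not between classes. The three clinical covariates are fixed pre-operative values, so as main effects they move a patient's level and not the change.

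The natural reading is that class is the exposure and the listed variables are adjusters. Class then enters as a main effect, and its coefficient is a difference in level averaged over the pre-operative and post-operative visits. A reader who trusts the heading would take that number for a difference in change. It can hide a real difference in change, or show one where there is only a pre-operative gap.

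**Working it through.** **Inputs.** From the documents: 50 patients (protocol summary), two classes (SAP) and three questionnaire visits (protocol section 3). The documents give no SD, correlation, class split, slope variance or target difference for this analysis, so there is no planned figure to reproduce and every other input below is an assumption. Visit times are taken as 0, 1.75 and 7.5 months.

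**1. What a class main effect estimates.** Let one class start g points above the other and improve by d points more at both post-operative visits. The class differences at the three visits are g, g + d and g + d. In a random-intercept model with complete data the visits carry equal weight, so, if the covariates do not absorb the gap, the class coefficient is g + 2d/3.

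| g | d (true difference in change) | class main effect |
|---|---|---|
| 0 | 15 | 0 + 10 = 10 |
| -10 | 15 | -10 + 10 = 0 |
| 10 | 0 | 10 + 0 = 10 |

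The first and third rows give the same coefficient, although the true difference in change is 15 in one and 0 in the other. A class-by-visit contrast returns d in every row.

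**2. With a random slope.** Take SD 22, correlation 0.6 and slope SD 2 points per month. The generalised least squares visit weights become about 0.45, 0.39 and 0.16, so the coefficient is about g + 0.547d. The first two rows become 8.2 and -1.8. The values move, but the gap and the change are still mixed.

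**3. Can the added term recover the difference?** In simulated studies (50 patients, 100 runs per scenario, two equal classes, random-intercept models fitted by maximum likelihood), true changes of 20 and 0 gave a mean class-by-time estimate of -20.0 against a true -20. True changes of 10 and 10 gave 0.60 against 0. Adding class only as a main effect left the time coefficient unchanged.

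**4. Time coding.** Suppose the 15-point difference is a step, present at both post-operative visits. The mean time is 3.083, so the deviations are -3.083, -1.333 and 4.417, with sum of squares 30.79. The linear slope is 15 × (-1.333 + 4.417) / 30.79 = 1.50 points per month, or 11.3 points at 7.5 months instead of 15.

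**5. Precision of the contrast from pre-operative to 6-9 months.** With SD 22 and correlation 0.6, the residual variance is 484 × 0.4 = 193.6. For complete data and slope SD s, SE = √[(2 × 193.6 + s² × 7.5²) × (1/25 + 1/25)]. The half-width uses t(48) = 2.01. The missing-data rows use generalised least squares on all observed visits, with questionnaires missing at random at 6-9 months.

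| Slope SD | Missing at 6-9 months | SE | 95% half-width |
|---|---|---|---|
| 0 | 0% | 5.57 | 11.2 |
| 2 | 0% | 7.00 | 14.1 |
| 0 | 30% | 6.33 | 12.7 |
| 2 | 30% | 8.02 | 16.1 |

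Missing data are plausible because the last questionnaire is posted: "A quality of life questionnaire will be mailed to patients with a self-addressed envelope".

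The best case (SD 18, correlation 0.8, s = 0, complete) gives √(2 × 324 × 0.2 × 0.08) = 3.22, or ±6.5. The worst case at 25+25 (SD 26, correlation 0.4, s = 2, 30% missing) gives SE 10.36, or ±20.8. Unequal classes widen this. For 40/10 the factor is √(0.125/0.08) = 1.25, giving ±26.0; for 35/15 it is 1.09, giving ±22.7.

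**6. Why the slope comparison should stay.** With s = 2, a random-intercept-only fit reports SE √[2 × (193.6 + 4 × 15.40) × 0.08] = 6.39, where 15.40 = 30.79/2, against a true 7.00. The nominal 5% test then runs at about 7.4%.

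**The case against.** The strongest reply is that this text is a short narrative in the past tense and not a model formula. It does not say that its list of terms is complete, a conditional growth model can carry predictors of the slope, and the remark about the intercept may be a loose gloss. The code may well have held class-by-time. That stands in part: the documents support a finding about what is stated, not about what was run. It does not remove the point, because the only description of the conditional step refers to the intercept and to covariate adjustment, and nothing else in either document supplies the term.

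Three stronger readings are tempting.

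- A reader might take the listed terms as the whole model, with class absent and a single pooled change estimated. The heading and the phrase about adjustment make class the natural exposure, so this is the less likely reading.
- A reader might infer that the section cannot answer its own question, or that the analysis was done wrongly. The documents do not show which terms were fitted.
- A reader might carry the problem over to the study's main conclusions. Section 3.1 of the protocol presents post-operative quality of life as pilot data, section 2 sets no objective on its change by class, and the SAP's primary outcome is functional capacity.

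**Conclusion.** The point holds as a gap in specification that matters for interpretation. Followed as written, with class as a main effect, the model does not estimate the between-class difference in change that the heading promises. A true 15-point difference could appear as 10 or as 0, depending on the pre-operative gap. Those exact values need a random intercept, complete data at three visits and a gap that the covariates do not absorb; with a random slope they shift but the mixing remains. The structural conclusion does not rest on any assumed number. Confidence is high that the term is missing from the text. Whether it was missing from the fitted model is unknown. The analysis is exploratory, so this should be fixed but threatens no primary result.

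**What to change.** In the conditional growth model, write class, time and class-by-time as fixed effects, with time as a three-level visit factor (pre-operative, 6-8 weeks, 6-9 months). Keep the listed covariates and the comparison of fixed with random slopes, with the random slope in months. Report the class-by-visit contrast from pre-operative to 6-9 months with its 95% CI, for physical functioning and for social functioning, as an exploratory estimate. If the models have already been fitted, state which class terms were used. If class-by-time was absent, refit and report the contrast as not pre-specified.

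The cost is a changed formula and a few words of text, with no new data. The model has five fixed-effect parameters for class and time (one class, two visit, two interaction) against one for a class-free model linear in time, so four more. The estimate will be imprecise, over the range worked out above, and suits an interval reported as pilot data. Refitting after the analysis does not restore pre-specification.

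### The only hypothesis test named in the quality-of-life section addresses neither change nor class of indication, and the growth models that could do so are given no test

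*SAP*

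**What the plan says.** The relevant SAP section is headed "Comparing changes in quality of life between class of indication of surgery". Its outcomes are two scales analysed as repeated measures: "Linear mixed effects models were fitted for longitudinal (repeated measures) outcomes (physical functioning and social functioning"). The models are "adjusted for time, preoperative percentage predicted peak VO2, preoperative LVEDD and preoperative LVESD".

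The modelling has three steps.

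- **Unconditional means model.** The SAP says "first, an unconditional means model was run to describe the data and to test the null hypothesis". It explains the role of this model as follows: "The unconditional mean model determines if the intercept is different from zero and if there is subjectrelated variability".
- **Growth models.** The SAP continues "then an Unconditional Growth Model to set up the slope has been run followed by a Conditional Growth model (to set up the intercept"). Fixed-slope and random-slope versions are both fitted in order to choose the better one.
- **Final model.** "The Conditional growth model is the final step and it is the complete final model adjusted for the covariates".

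The protocol names the SF-36 as the instrument (section 3, pre-operative investigations). It schedules the questionnaire before surgery, at 6-8 weeks and at 6-9 months (section 3, post-operative follow up, and Appendix 1). The planned population is 50 (Study Summary), and significance is declared at P<0.05 (section 7).

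**The concern.** The heading asks a between-class question about change. The single step described as a test contains neither time nor class, so no result from it can answer that question. Its intercept is the average score over patients and visits. If that average is positive, the hypothesis of a zero intercept is false before any data are collected.

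The growth models are described by what they set up, how well they fit and what they adjust for. No coefficient, contrast or model comparison in them is named as the inference. Class of indication, which the heading makes the comparison of interest, is absent from the listed terms.

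An analyst who follows the text literally would have one named test that is uninformative about the question. The test that is informative would have to be chosen later, with nothing prespecified to guide the choice.

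**Working it through.** The documents give no power, error rate, mean, SD or correlation for this analysis, so there is no figure of the plan's to reproduce.

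**Inputs from the documents.** n = 50; 3 assessments per patient; alpha 0.05 (sidedness not stated, two-sided assumed); maximum likelihood estimation.

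**Assumptions.** Uncentred scores on a 0-100 scale; mean, SD and intraclass correlation (ICC) as shown; in the simulation, two classes of equal size.

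**Step 1: the intercept test.** In a balanced random-intercept model with 3 visits:

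SE = SD × √[(ICC + (1 − ICC)/3)/n], z = mean/SE, power ≈ Φ(z − 1.96).

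With ICC 0.8, the least favourable value considered, n = 50 and SD 30:

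SE = 30 × √[(0.8 + 0.0667)/50] = 30 × 0.1317 = 3.95. A mean of 50 gives z = 50/3.95 = 12.7.

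| n | Mean | SD | z | Power |
|---|---|---|---|---|
| 50 | 50 | 30 | 12.7 | 1.000 |
| 50 | 30 | 30 | 7.6 | 1.000 |
| 50 | 30 | 40 | 5.7 | 0.9999 |
| 50 | 20 | 40 | 3.8 | 0.967 |
| 20 | 20 | 40 | 2.4 | 0.671 |

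Rejection falls clearly below certainty only when a low mean is combined with a very large SD, and mainly in a small sample.

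**Step 2: which terms respond to change.** Mixed models were fitted by maximum likelihood to simulated data (200 replicates per setting, scores truncated to 0-100). The first three settings use n = 50, mean 60, SD 25, ICC 0.5. The fourth uses n = 20, mean 30, SD 30, ICC 0.5. Entries are the percentage of samples with P<0.05.

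| Truth | Intercept = 0 (means model) | Time slope (growth model) | Class × time (class added) |
|---|---|---|---|
| No change, n = 50 | 100 | 4.5 | 8 |
| Same change in both classes, 5 points per visit | 100 | 78 | 3.5 |
| Change in one class only, 8 points per visit | 100 | 59.5 | 61 |
| No change, n = 20 | 100 | 4 | 5 |

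With 200 replicates, the standard error around a true 5% is √(0.05 × 0.95/200) = 1.5 percentage points, so 8% is about two standard errors from nominal.

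The intercept test gives the same answer in every row. The slope responds to change. Only class × time separates change common to both classes (3.5%) from change that differs between them (61%).

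**Step 3: the variance part of the means model.** Whether patients differ from one another is not settled in advance in the way the intercept test is. A between-patient variance still says nothing about change or class.

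**The case against.** The strongest reply is that the means model is only the first step, and partly a descriptive one. The sequence ends in a conditional growth model that the SAP calls complete and final. Time is among the adjustment terms, so that model has a time coefficient, and the protocol's general P<0.05 rule could be applied to it. This stands. In the simulation the slope behaved properly: 4.5% rejection under no change and 78% under a common change of 5 points per visit. It does not supply a named test, and it does not bring class into the model.

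A second reply is that the null hypothesis mentioned may include the variance component, since the SAP gives the means model two purposes. That is also fair. The intercept is only half of what the model is said to assess, and a zero mean score is an interpretation that depends on the outcomes being uncentred scores. The SAP mentions neither centring nor change scores.

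A reader might infer more: that the whole quality-of-life analysis rests on the intercept test, and that a positive finding would be reported whatever surgery did. The documents do not support this. They do not say that an intercept P value will be reported as a result or read as improvement. Nor is this the main analysis of the study: the SAP's primary outcome is reduced functional capacity at follow up.

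**Conclusion.** The point holds as a defect of specification. The one test the section names cannot address the section's question. No test of time or class by time is named, and class is missing from the listed terms.

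The intercept test rejects in about 100% of samples under plausible means and SDs, whether or not quality of life changes. That figure rests on assumed score distributions and uncentred outcomes, and it weakens in extreme settings (0.671 at n = 20, mean 20, SD 40). The structural point does not depend on those assumptions, because a model without time or class cannot test either.

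The planned growth models remain usable. What is missing is the class term and a statement of which coefficient carries the inference.

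**What to change.** In the SAP's quality-of-life section:

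1. Remove the hypothesis-testing role from the unconditional means model. Keep it as descriptive: mean, variance components and ICC.
2. Add class of indication and class × time to the conditional growth model, and state how time is coded over the three assessments.
3. Name the class × time test, the between-class difference in change, as the inference for the question in the heading.
4. Name the time effect, or the 6-9 month minus pre-operative contrast, as the test of overall change.
5. Give an estimate and 95% CI for each, and report no intercept P value as a finding.

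A test of time alone would not be enough, because it does not compare classes.

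No new data are needed. If class has two levels, as in the SAP's baseline comparisons, the addition is two parameters with linear time (class, class × time) or three with visit as a category (1 + 2). The real cost is precision. Under the assumptions above, with 50 patients in two equal classes, a difference of 8 points per visit was detected in 61% of samples. The class × time estimate should therefore be read mainly through its confidence interval.
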